7.2 Evaluation of non-target lesions

Complete Response (CR):	Disappearance of all non-target lesions and normalization of tumor marker level
Incomplete Response/ Stable Disease (SD):	Persistence of one or more non-target lesion(s), and/or maintenance of tumor marker level above the normal limits
Progressive Disease (PD):	Appearance of one or more new lesions, and/or unequivocal progression of existing non-target lesions

Although a clear progression of non-target lesions only is exceptional, in such circumstances, the opinion of the treating physician should prevail and the progression status should be confirmed later on by the study chair.

7.3 Evaluation of best overall response

The best overall response is the best response recorded from the start of the treatment until disease progression/recurrence (taking as reference for progressive disease the smallest measurements recorded since the treatment started, including baseline; see table below). The patient's best response assignment will depend on the achievement of both measurement and confirmation criteria.

7.4 Confirmation

To be assigned a status of PR or CR, changes in tumor measurements must be confirmed by repeat studies no less than 4 weeks after the criteria for response are first met. In the case of SD, follow-up measurements must have met the SD criteria at least once after study entry at a minimum of 12 weeks after study entry.

7.5 Duration of Overall Response

The duration of overall response is measured from the time measurement criteria are met for CR/PR (whichever is first recorded) until the first date that recurrent or progressive disease is objectively documented (taking as reference for progressive disease the smallest measurements recorded since the treatment started). The duration of overall complete response is measured from the time measurement criteria are first met for CR until the first date that recurrent disease is objectively documented.

Target Lesions	Non-Target Lesions	New Lesions	Response
CR	CR	No	CR
CR	Incomplete response/SD	No	PR
PR	Non-PD	No	PR
SD	Non-PD	No	SD
PD	Any	Yes or No	PD
Any	PD	Yes or No	PD
Any	Any	Yes	PD

7.6 Evaluation of non-measurable bone disease per PCWG Criteria

Bone scans obtained after the baseline evaluation will be used to evaluate post-treatment changes. Bone scans obtained will be evaluated as either "no new lesions" or "new lesions" on the tumor measurement forms.

- For the first scheduled reassessment: New lesions at the first scheduled evaluation (9 weeks) will require a confirmatory bone scan 6 or more weeks later. If no new lesions are observed on the confirmatory bone scan, study therapy is continued. If additional new lesions are observed, then the patient has experienced progression. Progression in this situation is dated as the time of the first reassessment scan.

- b. For subsequent scheduled reassessments: If no new lesions are observed, study therapy will continue. If new lesions are observed, this is evidence of disease progression. Date of progression is the date at which the scan was obtained.

7.7 Post-treatment PSA Changes

All patients will be evaluated for PSA decline. Patients with disease that is not measurable will be eligible for this study and will be assessed for response based on changes in PSA and serial bone scans (if appropriate). The baseline serum PSA must be at least 2 ng/mL. Patients who show PSA increases will not be evaluated for PSA progression prior to 12 weeks of study therapy.

- a. 30% and 50% PSA Decline: PSA decline of at least 30% and 50%, respectively, from baseline confirmed by a second measurement at least 3 weeks later. The reference for these declines should be a PSA measured within 2 weeks prior to starting therapy.
- b. PSA Progression: Prostate Cancer Working Group 2 (PCWG2) Criteria will be reported. PSA progression occurs when the PSA has increased 25% or greater above nadir and an absolute increase of 2 ng/mL or more from the nadir is documented. Where no decline is observed, PSA progression similarly occurs when a 25% increase from baseline value along with an increase in absolute value of 2 ng/mL or more. Patients will receive a minimum of 12 weeks of therapy prior to being evaluable for this endpoint. PSA progression (without evidence of progression on scans) will not be criteria for discontinuation of study therapy.
- c. PSA Response Duration: The PSA response duration commences on the date of the first 50% decline in PSA. The response duration ends when the PSA value increases by 25% above the nadir, provided that the increase in the absolute-value PSA level is at least 5 ng/mL or back to baseline, whichever is lower.
- d. Progressive Disease by PSA (as defined by PSA Progression, above)
- e. Time to PSA Progression: The start of the time to PSA progression is the day treatment is initiated. The end date is the date of the first PSA rise over the determined PSA PD value.

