8.4.2 Analytic Plan for Secondary Endpoints

Median duration of response

Median duration of response will be estimated using Kaplan-Meier product limit method, starting with the date of first scan indicating response until loss of response or progression, or death, whichever occurs first.

PSA response rate

The proportion of patients who achieve a greater than 50% decline from baseline PSA drawn on C1D1, at any point in the treatment course, will be descriptively reported along with 95% confidence interval.

PSA progression free survival

PSA progression will be defined using PCWG3 criteria. Median PSA progression free survival will be estimated using the Kaplan-Meier method. Duration will be measured from date of first treatment to date of first PSA meeting criteria for PSA progression.

Time to symptomatic skeletal related event

Symptomatic skeletal related event is defined as the first occurrence of one or more of the following: symptomatic fracture, surgery or radiation to bone, or spinal cord compression. The median time to symptomatic skeletal related event will be determined using Kaplan-Meier method.

Safety

The incidence and severity of adverse events related to study treatment will be descriptively reported using CTCAE v4.0.

Radiographic progression free survival and 6-month rPFS rate:

Radiographic progression of disease will be defined by RECIST v1.1 and PCWG3 criteria. For the first scheduled reassessment by bone scan (at Cycle 2), new bone lesions will require a confirmatory bone scan 6 or more weeks later. Median PFS will be estimated using the Kaplan-Meier method. Durations will be measured from the first day of study treatment (Cycle 1) to the first date of radiographic progression or death, whichever occurs first. Patients who discontinue study treatment for toxicity, withdraw from the study, or have PSA-only progression will be censored at the date of the last radiographic tumor assessment. Patients who discontinue treatment for clinical progression or deterioration will be included in the analysis.

Overall survival

Median overall survival and 95% confidence interval will be estimated using the Kaplan-Meier method. Duration will be measured from first date of study therapy to date of death from any cause.

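### PSA progression is written without a confirming value and under two different PCWG versions, so measurement noise can create false events and shorten the median PSA progression-free survival

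*Combined protocol and SAP*

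**What the plan says.** Section 2.1 lists median PSA progression-free survival as a secondary objective. The event is defined in section 7.7 and analysed in section 8.4.2.

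- **Threshold (7.7b):** "PSA progression occurs when the PSA has increased 25% or greater above nadir and an absolute increase of 2 ng/mL or more". For patients whose PSA never falls: "Where no decline is observed, PSA progression similarly occurs when a 25% increase from baseline value", again with at least 2 ng/mL in absolute terms.
- **Early guard (7.7b):** "Patients will receive a minimum of 12 weeks of therapy prior to being evaluable for this endpoint".
- **Date (7.7e):** "The end date is the date of the first PSA rise over the determined PSA PD value". Section 8.4.2 agrees: "Duration will be measured from date of first treatment to date of first PSA meeting criteria for PSA progression".
- **Criteria named:** "Prostate Cancer Working Group 2 (PCWG2) Criteria will be reported" in 7.7b, but "PSA progression will be defined using PCWG3 criteria" in 8.4.2. Neither set is reproduced.

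Other endpoints in the same plan carry a confirmation step. A PSA decline must be "from baseline confirmed by a second measurement at least 3 weeks later" (7.7a). CR and PR need repeat imaging at least 4 weeks later (7.4, 8.4.1). New bone lesions at the first reassessment need a repeat scan at least 6 weeks later (7.6a). PSA progression has no such step in the text.

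**The concern.** Nadir is the lowest of several noisy measurements, so it tends to sit below the patient's true level. Each new PSA is another chance to land 25% above it. With no repeat value required, one high reading after one low reading is enough to end the interval. Such errors all shorten time to PSA progression.

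The two PCWG labels add a second problem. An analyst who follows the words of 7.7b and one who follows the published criteria named in 8.4.2 may not derive the same events, and the documents do not show whether the two agree.

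At stake is the reliability of one secondary summary, the Kaplan-Meier median of PSA progression-free survival.

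**Working it through.** The plan states no expected median, power or sample size for this endpoint, so there is no figure of its own to reproduce.

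**Inputs from the documents.** The 25% and 2 ng/mL thresholds and the 12-week guard come from 7.7b. PSA is drawn on Day 1 of each 21-day cycle, about every 3 weeks (study calendars 5.2 to 5.4).

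**Assumed.** Within-patient CV of 5% to 20%; log-normal noise, independent between draws.

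**Step 1: where the 2 ng/mL guard bites.** It is the stricter condition when 0.25 × nadir < 2, that is, nadir < 8 ng/mL. Above that, the 25% rule decides.

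**Step 2: one pair of values.** The log-scale SD is σ = √ln(1 + CV²). The chance that one value exceeds another by 25% with no true change is 1 − Φ(ln 1.25 / (σ√2)).
- CV 5%: σ = 0.0500, z = 0.2231 / 0.0707 = 3.16, probability 0.08%.
- CV 10%: σ = 0.0998, z = 0.2231 / 0.1411 = 1.58, probability 5.7%.

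At week 12 the comparison is with the lowest of four earlier values (weeks 0, 3, 6, 9). At CV 10% the simulated probability rises to 16% (5% if the next value must also qualify). By week 27 there have been six looks (weeks 12, 15, 18, 21, 24, 27).

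**Step 3: truly flat PSA.** Simulation of 40,000 patients per setting. An event is the first value from week 12 that is at least 1.25 × the running minimum and at least 2 ng/mL above it. Confirmed means that the next 3-weekly value also passes the same limits, with the event dated at the first rise.

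False progression by week 27:

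| Setting | CV | As written | Confirmed |
|---|---|---|---|
| PSA 10 or more | 5% | 2% | 0.1% |
| PSA 10 or more | 8% | 41% | 10% |
| PSA 10 or more | 10% | 66% | 26% |
| PSA 10 or more | 15% | 92% | about 60% |
| PSA 5 | 10% | 7% | 0.2% to 0.3% |
| PSA 10 or more, baseline as reference until a 30% fall | 10% | about 24% | 7% |

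The last row takes 7.7b's no-decline clause to cover every patient who has not reached the smallest decline that 7.7a defines.

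**Step 4: PSA that falls and regrows.** Assumed: a 60% fall by week 6, a plateau of mean 20 weeks, then a doubling time of 9 weeks. The noise-free median is 24 weeks.

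| CV | Median as written | Median confirmed |
|---|---|---|
| 5% | 24 | 24 |
| 8% | 21 | 21 |
| 10% | 18 | 21 |
| 15% | 15 | 18 |
| 20% | 15 | 18 |

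Confirmation moves the median by 0 to 3 weeks. At CV 10% the bias falls from 24 − 18 = 6 weeks to 24 − 21 = 3 weeks; it does not vanish. A second assumed population, with varied depth of decline and median doubling times of 12 to 40 weeks, gave shifts of 0 to 6 weeks, never earlier; the 6-week shifts needed CV 15% or more and slow regrowth.

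**The case against.** Several points on the other side are sound.

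- **The named criteria may require confirmation.** Both sections tie the endpoint to published criteria. The documents do not reproduce them, so one cannot conclude that the endpoint will be analysed unconfirmed. What stands is narrower: the written rule omits the step, and two versions are named.
- **The dating rules prove nothing.** 7.7e and 8.4.2 date the event at the first qualifying PSA. A confirmed rule dated at the first of two rises fits that wording. The gap lies in 7.7b.
- **Guards exist.** The 12-week rule excludes early rises, and the 2 ng/mL rule protects patients with a nadir below 8 ng/mL. Both are in the simulation; neither stops later false events at higher PSA.
- **Flat PSA is not the typical case.** Entry requires progressive disease (3.3). The regrowth results are the fairer guide, and they are much smaller.

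Two stronger readings are tempting. A reader might infer that noise will make stable patients progress. That holds only if the CV is well above 5%, and nothing in the documents favours 10% over 5%.

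A reader might also infer that the rule hides a prolongation over the 6.3 months quoted for Lu-PSMA alone in section 1.3. The documents do not support this: they do not say whether that study confirmed PSA rises, and 8.4.2 plans no test against it. If that figure rests on unconfirmed rises, adding confirmation here would tilt an informal comparison towards the combination. Its interval of 4.8 to 8.3 months, from 30 patients, is also wide beside a 3-week shift (3 / 4.345 = 0.7 months).

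**Conclusion.** The concern holds as a minor point. The written definition lacks a confirming value that the same section requires for PSA decline, and the two sections name different PCWG versions. The direction of the error is known: false events come early, and the median can only be pulled down.

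The size is not known. It is negligible at CV 5% and large in flat patients at CV 10%. It shrinks when PSA is low or baseline is the reference. In the main regrowth model, confirmation changes the median by at most one 3-week sampling interval. All of this rests on an assumed CV, on noise that is independent between draws, and on assumed PSA trajectories. If fluctuations persist from one draw to the next, confirmation will help less.

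The consequence is confined to PSA progression-free survival, which is a secondary objective in 2.1 but is absent from the endpoint list in 2.2.2. PSA-only progression does not stop treatment (3.4, 5.1) and is not progressive disease (7.8). The Part B objective response design in 8.1 is untouched.

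**What to change.** In 7.7b, require the rise (at least 25% and at least 2 ng/mL above nadir, or above baseline where there was no decline) to be confirmed by a second PSA at least 3 weeks later, and date the event at the first of the two rises. The dating rules in 7.7e and 8.4.2 can then stand. Name one PCWG version in both sections. Where a rise occurs at the last available PSA and cannot be confirmed, count it as an event in a sensitivity analysis. It would also help to say what counts as no decline, since the choice of reference changes the results in Step 3.

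The cost is wording only. PSA is already drawn each cycle and patients with PSA-only progression stay on treatment, so the confirming value will normally exist. The one drawback is the small number of last-visit rises, which the sensitivity analysis covers.

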7.8 Progressive disease (PD)

Progressive disease will be defined by any one of the following:

1. Appearance of new metastatic lesions outside the bone
2. New metastatic lesions on bone scan confirmed as described above
3. Development of an indication for radiotherapy while on treatment
4. Unequivocal progression of non-target lesions
5. Global deterioration of health status requiring discontinuation of treatment without objective evidence of disease progression

Note that PSA progression (as defined above) alone does not meet the criteria for progressive disease.

8 Statistical Considerations

8.1 Sample Size Justification

The sample size determination is based on the primary endpoints of the study, to determine the maximally tolerated and recommended phase 2 dose and schedule of the combination. 6 patients will be enrolled at each of the three planned cohorts in Part A of the study. Therefore, up to 18 evaluable patients total will be enrolled in Part A.

In Part B, the primary efficacy endpoint is objective response rate by RECIST 1.1 criteria. A sample size of $N = 25$ patients is chosen to provide a preliminary estimate of the response rate with the recommended phase 2 dose and schedule of ^{177}Lu -PSMA-617 in combination with pembrolizumab. Using a historical control objective response rate with pembrolizumab monotherapy in mCRPC of 10% (e.g. KEYNOTE-028 study, in press Annals of Oncology), and an alternative hypothesis of ORR = 40%, a sample size of 25 patients provides 93% power to detect a difference of this magnitude in ORR with a bi-directional level of significance of 0.05.

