Rationale for Study	
Despite recent advances in the treatment of mCRPC, including the approval of novel agents such as sipuleucel-T, abiraterone acetate, enzalutamide, and radium-223, patients with mCRPC have a poor prognosis and many eventually succumb to their disease. Patients with abiraterone and/or enzalutamide refractory mCRPC represents a particularly challenging subgroup of patients who have limited effective treatment options other than chemotherapy.
 
Prostate-Specific Membrane Antigen (PSMA) is a cell surface protein overexpressed on most prostate cancer cells, especially in advanced stage disease. The safety and efficacy of ¹⁷⁷Lu radiolabeled PSMA has been reported in several studies, including a recent prospective phase 2 study (Hofman et al. 2017). In patients with PSMA-avid metastatic disease, the PSA response proportion and objective response rate by RECIST 1.1 range from 40-60%, in heavily pre-treated patients. However the response duration is short, and therefore novel treatment strategies are needed to maintain and extend the duration of response achieved.
 
We propose to utilize immune checkpoint inhibition with pembrolizumab as a means to maintain anti-tumor response. We leverage a robust body of literature indicating that radiotherapy induces an immunogenic response, in the form of induction of infiltrating T cells, broadening of the T cell repertoire, and induction of PD-L1 expression, facilitating subsequent treatment with immune checkpoint inhibitor.
 
In the current study we will obtain the preliminary safety and efficacy data of ¹⁷⁷Lu-PSMA-617 radioligand therapy (RLT) in combination with pembrolizumab in patients with metastatic castration resistant prostate cancer. Favorable results with respect to toxicity and preliminary evidence of efficacy would form the basis for a subsequent definitive randomized study of the treatment combination in PSMA-expressing metastatic castration-resistant prostate cancer.

Primary Objectives	
Part A: To determine the recommended phase 2 dose and schedule of ¹⁷⁷Lu-PSMA-617 in combination with pembrolizumab in patients with mCRPC.
 
Part B (Dose Expansion): To determine the objective response rate by RECIST 1.1 criteria.

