Despite the significant anti-tumor activity with Lu-PSMA RLT, there are several significant limitations of this approach as monotherapy: 1) There is significant **heterogeneity of PSMA expression**, both in analysis of individual circulating tumor cells as well as diagnostic PSMA PET imaging of metastatic lesions across individual patients, and 2) Within PSMA-avid lesions, there is a **limited duration of response**. In a recently presented prospective phase 2 study of Lu-PSMA, despite enriching for patients with more homogenous level of PSMA uptake on baseline PET imaging, the median PSA progression-free survival by PCWG criteria was only 6.3 months (95% CI 4.8 – 8.3), and median overall survival only 12.7 months. Nearly half of the 30 patients enrolled received less than the pre-specified 4 doses of Lu-PSMA treatment, for both toxicity-related reasons (hematologic, salivary gland) as well as rapid disease progression following initial response. The reasons for rapid disease progression include baseline heterogeneity of PSMA expression among disseminated tumor cells, leading to diffuse bone marrow involvement in a subset of patients. There is a clear and unmet medical need to merge the rapid anti-tumor responses achieved by Lu-PSMA RLT with a treatment that can both sustain and spread response to PSMA-negative lesions without excess cumulative toxicity.

Immune checkpoint inhibition, by virtue of antigen spread induced by immunogenic cell death induced by antecedent radioligand treatment, may accomplish this goal.

1.4 Immune Checkpoint Inhibition Leads to Durable Responses in a Minority of mCRPC Patients

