Single agent immune checkpoint inhibitor treatment, including therapies blocking PD-L1/PD-1 as well as CTLA-4 mediated signaling, have demonstrated that durable anti-tumor responses can be achieved in mCRPC. Immune checkpoint inhibitors including ipilimumab and pembrolizumab have led to durable tumor responses in a limited number of cases in mCRPC, but increasing the proportion of patients who respond to single agent checkpoint blockade has been challenging. [name] at UCSF led the first in human study of ipilimumab in mCRPC. Overall, the tumor immunogenicity, as reflected by mutational burden, tumor infiltrating lymphocytes, and tumor PD-L1 expression, are low in prostate tumors relative to other tumor types such as melanoma. In the KEYNOTE-028 study of pembrolizumab in mCRPC patients, the tissue screen positivity rate for PD-L1 expression in archival tumor tissue was less than 10%, and even in PD-L1 positive tumors, the objective response rate by RECIST 1.1 criteria was only 17%. However, in those patients who experienced a tumor response, there was durable regression of disease with median duration of response of over 15 months. For the majority of mCRPC patients who do not benefit from single agent immune checkpoint inhibitors, there is an unmet medical need to enhance tumor immunogenicity with priming therapy to enhance TILs, induce PD-L1 expression, and expand the T cell repertoire, thereby translating into a significant improvement in proportion of patients achieving durable tumor response.

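### Does powering Part B against pembrolizumab alone (10%) undermine the justification for 25 patients, given that every patient also receives Lu-PSMA?

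*Combined protocol and SAP*

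**What the plan says.** Section 8.1 gives two supports for the size of Part B. First, N = 25 "is chosen to provide a preliminary estimate of the response rate" with the chosen dose and schedule. Second, it takes a reference rate ("Using a historical control objective response rate with pembrolizumab monotherapy in mCRPC of 10" per cent), sets the alternative at 40%, and states that "a sample size of 25 patients provides 93% power to detect a difference of this magnitude" at a two-sided level of 0.05.

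Other parts of the document bear on how to read this:

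- Section 3.2: the study is not randomized, and all Part B patients receive both agents. Section 3.5: patients who withdraw before the Lu-PSMA dose are replaced.
- Synopsis, Rationale for Study: for Lu-PSMA in PSMA-avid disease, "the PSA response proportion and objective response rate by RECIST 1.1 range from 40-60%, in heavily pre-treated patients". The same entry says that favorable toxicity results and "preliminary evidence of efficacy would form the basis for a subsequent definitive randomized study of the treatment combination".
- Section 1.4: few patients respond to checkpoint inhibition alone, and priming is proposed as the way to raise that number, "translating into a significant improvement in proportion of patients achieving durable tumor response".
- Section 8.4.1: the Part B response rate is reported descriptively with a 95% confidence interval. No hypothesis test or success threshold is declared.

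**The concern.** The regimen has two active parts, and section 8.1 measures it against a historical rate for only one of them. The 40% alternative is also the bottom of the range that the synopsis gives for the other part. If Lu-PSMA alone produced 40% in these patients and pembrolizumab contributed nothing, Part B would still be very likely to exceed 10%. A reader who meets only section 8.1 could take such a result as support for the combination.

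Section 1.7 says that the data will inform whether to proceed to a phase 2/3 study, so a misreading could matter. Section 8.1 does not mention the limit. The power figure also seems to belong to a test that section 8.4.1 does not plan.

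**Working it through.** **Inputs.** From section 8.1: n = 25, null rate 0.10, alternative 0.40, two-sided 0.05 (0.025 in the upper tail). From the synopsis: 40-60% for Lu-PSMA. Assumed, because the documents give no response rate after a single Lu-PSMA dose: 20%, 25%, 30% and 35%.

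**1. The stated power.** With X ~ Binomial(25, p), find the smallest r for which P(X ≥ r | 0.10) ≤ 0.025.

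- P(X ≥ 6 | 0.10) = 0.0334, too large.
- P(X ≥ 7 | 0.10) = 0.0095, so r = 7.
- Power = P(X ≥ 7 | 0.40) = 0.926, which rounds to the stated 93%.

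**2. Does the power relate to the planned analysis?** A 95% confidence interval excludes 10% exactly when the matching two-sided 0.05 test rejects 10%. Section 8.4.1 names no interval method. With the exact (Clopper-Pearson) interval:

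| Responders | Observed rate | Exact 95% CI | Excludes 10%? |
|---|---|---|---|
| 6/25 | 24% | 9.4% to 45.1% | No |
| 7/25 | 28% | 12.1% to 49.4% | Yes |

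The lower limit passes 10% at 7/25, the same rule as in step 1. The 93% can therefore be read as the chance, at a true rate of 40%, that the planned interval lies above 10%.

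**3. Chance of exceeding 10% if pembrolizumab added nothing.** This is P(X ≥ 7 | p), with p the true rate for Lu-PSMA alone in this population.

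| p | Source | P(X ≥ 7) |
|---|---|---|
| 20% | assumed | 22.0% |
| 25% | assumed | 43.9% |
| 30% | assumed | 65.9% |
| 35% | assumed | 82.7% |
| 40% | synopsis, lower end | 92.6% |
| 50% | synopsis, middle | 99.3% |
| 60% | synopsis, upper end | 99.97% |

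**4. Which row applies?** The documents do not say. The 40-60% range merges PSA response with RECIST response and refers to heavily pre-treated patients, whereas section 3.3 excludes taxanes given in the castration-resistant setting. The phase 2 study described in section 1.3 selected patients ("despite enriching for patients with more homogenous level of PSMA uptake on baseline PET imaging"). It also planned repeated dosing: nearly half of its patients "received less than the pre-specified 4 doses of Lu-PSMA treatment". Section 1.7.1 plans one dose here. Section 1.3 says that responses are often seen after one dose, but gives no rate.

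**5. Precision of the estimate.** At 10/25 = 40% the exact 95% CI is 21.1% to 61.3%. The widest interval at n = 25 is 41 percentage points (for example 13/25 = 52%, CI 31.3% to 72.2%). That is adequate for a preliminary estimate, and the plan claims no more.

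**The case for a change.** The strongest case for a change is that section 8.1 gives only the 10% rate, that Part B feeds a decision on further development, and that a sentence or two would close off a wrong reading. If the true Lu-PSMA rate here were 40% or more, exceeding 10% would be close to certain and would say nothing about pembrolizumab's contribution. The main effect expected of pembrolizumab in section 1.7 is durability, which is assessed by secondary endpoints and not by the response rate.

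The statistical core of this stands: a single arm in which everyone receives both agents cannot separate them, at any sample size. Three things weaken the case for acting on it.

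- The document does not draw the inference. Section 8.1 says outright that the reference is pembrolizumab monotherapy, no section makes 10% a threshold for going on, and the synopsis assigns the definitive answer to a randomized study. The synopsis also prints the 40-60% range, so a reader has that context.
- The comparator answers a question the protocol asks. Section 1.4 is about raising a low checkpoint-inhibitor response rate by priming, and pembrolizumab alone is the natural reference for primed pembrolizumab.
- The 40-60% range could not replace it as a control rate, for the reasons in step 4.

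The argument that the 93% belongs to no planned analysis mostly falls. No formal test is declared, but by step 2 the figure corresponds to the planned interval if that interval is exact.

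**Conclusion.** No change is needed. The sample size, the power figure, the endpoint and the descriptive analysis are sound as written. The stated 93% is correct (exact 92.6%, 7 or more of 25). An observed rate above 10% would bear on whether the regimen does better than the historical rate for pembrolizumab alone. It would not show that pembrolizumab adds to Lu-PSMA, and the protocol does not say that it would.

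The chance of passing 10% on Lu-PSMA alone lies between 22% and 99.97% for true rates of 20% to 60%. The lower part of that range is assumed and the upper part comes from a setting that is not like-for-like, so the documents do not settle the size of the problem. The link between the 93% and section 8.4.1 assumes an exact interval.

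A sentence on attribution, or a statement of precision in place of power, would be harmless, but it would only restate what the single-arm design and the named comparator already make plain. An analyst reporting Part B would give the proportion with its interval and treat it as preliminary, as section 8.4.1 and the synopsis already provide.
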